### Craving.

The 10-item brief QSU questionnaire on smoking urges (Cox et al., 2001) will be used to assess craving for cigarettes during the medication run-up period. The QSU-B contains 2 subscales (anticipation of reward, relief from negative affect). Craving has also been related to long-term cessation outcome in many, but not all, clinical studies (Killen and Fortmann, 1997). This will be administered at all study visits (except Intake; remotely or in-person). Similar to withdrawal symptoms, craving will be assessed using a 24-h time reference at all visits following the Intake.

### Sleep Quality.

The Pittsburgh Sleep Quality Index (PSQI) is a 9-item measure that assesses the quality and patterns of sleep over the past month. It measures seven areas: subjective sleep quality, sleep latency, sleep duration, habitual sleep efficiency, sleep

disturbances, use of sleep medication, and daytime dysfunction. Scoring is based on a 0 to 3 scale, whereby 3 reflects the negative extreme. A sum of 5 or greater indicates a poor sleeper (Buysse et al., 1989). The PSQI has good internal consistency (Cronbach's alpha=0.83), validity, and reliability, and is sensitive to treatment (Backhaus et al., 2002; King et al., 1997). The outcome is the global PSQI score.

#### Social Support.

Social support during a smoking cessation attempt will be assessed with the abbreviated Partner Interaction Questionnaire (PIQ; Cohen and Lichtenstein, 1990). This 20-item version of the PIQ asks participants to rate the degree to which they expect certain behaviors from their spouse/partner, friend, or relative. It assesses for both positive (e.g., helps you think of substitutes for smoking) and negative behaviors (expressed doubt about your ability to quit/stay quit).

#### Alternative Reinforcers.

A 45-item version of the Pleasant Events Schedule (PES) (MacPhillamy and Lewinsohn, 1982) will be used to measure traditionally rewarding activities that occur in a person's natural environment (Audrain-McGovern et al., 2011). The cross-product score of frequency (0=none to 2=often) and level of enjoyableness (0=none to 2=very) for each item provides a measure of activity reward. Participants are also asked whether they associate the activity with smoking or the urge to smoke. If the activity is associated with smoking, it is considered a complementary reinforcer. If the activity is not associated with smoking, it is considered a substitute reinforcer. The cross products of substitute reinforcers are summed to provide a score for substitute alternative reinforcers and those for complementary reinforcers are summed to provide a score for complementary alternative reinforcers. Scores have been associated with depression (Audrain-McGovern et al., 2011), discriminate between ex-smokers and current smokers, and predict smoking abstinence in cessation treatment (Audrain-McGovern et al., 2009; Goelz et al., 2014).

#### Risks and Benefits of Quitting.

The 40-item PRBQ (McKee et al., 2005) uses a 7-point Likert Scale (1=no chance, 7=certain to happen) to assess the likelihood of six potential risks and six potential benefits of quitting occurring if the participant were to stop smoking. The risk subscales were: 1) Weight Gain (I will gain weight.); 2) Negative Affect (I will be more irritable.); 3) Difficulty Concentrating (I will be less able to concentrate.); 4) Social Ostracism (I will feel uncomfortable around smokers.); 5) Loss of Enjoyment (I will miss the taste of cigarettes.); 6) Craving (I will desire a cigarette.). The benefits subscales were: 1) Health; 2) Well-being; 3) Self-esteem; 4) Financial; 5) Physical Appeal; and 6) Social Approval.

Subjective Cognitive Complaints. The PROMIS (Patient-Reported Outcomes Measurement Information System) is a set of person-centered measures that evaluates and monitors physical, mental, and social health in adults and children. The PROMIS Short Form v2.0 Cognitive Function Abilities Subset 8a will be used to assess subjective cognitive complaints. Each of the 8 items are scores from 1 (Not at all) to 5 (Very much). This measure has been validated in medical outpatient samples (Saffer et al., 2015) and among those living with HIV (Solorio et al., 2016).

#### Treatment Measures.

##### Concomitant Medication Review.

Subjects will be asked about their use of medications (over the counter and prescription) and substances that may alter subjects' response to the study medication. The Study Physician/Health Care Provider will advise as to whether other medications being taken are contraindicated and prescribe appropriate action from there (i.e., discontinuation of the study medication). The concomitant medication review will be completed at every study visit following the Intake.

##### TN Adherence.

We will assess self-reported use of patches and may collect unused patches (if applicable) when participants report to our center for study tasks. Any patch adherence that was not collected during the treatment period will be collected at the follow-up assessment at Week 12.

### Side Effects.

A checklist of side effects based on the product insert will be administered to participants at all study visits after the Intake. Checklists will be reviewed by staff following completion to confirm participant description of any experienced side effect matches the severity chosen, based on the severity classifications outlined on the form. The frequency and severity of common side effects of TN (Schnoll et al., 2015; Schnoll et al., 2010) will be rated on a 0 (none) to 3 (severe) scale. An open-ended side effects question will also be included. Furthermore, participants will receive written instructions to call the Health Care Provider/Study Physician should they experience any severe side effects or adverse events between study visits. There are no known HAART/TN interactions.

### Neurocognitive Outcomes

Neuropsychological tests will be administered in a quiet laboratory testing room on a Dell® desktop computer running the most recent and compatible version of Windows® at the CIRNA. Unless otherwise noted, all tasks will be administered via E-Prime 2.0 (Psychology Software Tools, Inc.). The computerized battery is administered in a random order using clickable icons. Total administration time is about 30 minutes. The outcomes and associated tasks are:

Executive Function. Two tasks will be used to assess executive function: a working memory N-Back task and the Stroop test. In the traditional N-back task, sequences of letters or numbers are displayed, and subjects respond with a button press to a single target using the following rules. During the 1-back condition, subjects respond if the image is identical to the one preceding it. In the 2-back condition, they respond if the stimulus is identical to the one two trials before. In the 3-back condition they respond if the image is identical to the one three trials before. The version of the N-back used in this study utilizes fractal images in place of letters or numbers. The active baseline condition (0-back) is a simple target detection task. The primary outcomes will be total correct and correct reaction time (task duration: about 18 minutes).

The Stroop test will be used to assess executive function. In the Stroop test (Stroop, 1935), participants view a series of words on a computer monitor and using the keyboard, are asked to press the key associated with the color of the word rather than the word itself. Congruent trials are trials in which the word and color match (e.g., the word "green" appears in the color green). Incongruent trials are trials in which, the words are printed in colors that do not match the colors of the words (e.g., the word "red" might appear in green). The primary outcome is the interference score, which is the reaction time to incongruent trials minus the reaction time to congruent trials and measures the ability to suppress a habitual response in favor of an unusual one, accounting for overall speed of naming. Task duration is 5 min.

Verbal Learning and Memory. The Hopkins Verbal Learning Test – Revised (HVLT-R) assesses verbal learning and memory (immediate recall, delayed recall, delayed recognition) (Brandt, 1991). The task has been validated in individuals 16 to 92 years old and within brain-disordered populations (e.g., Alzheimer's disease, amnestic disorders) as a measure of verbal learning and memory (Benedict et al., 1998). There are six alternate forms, each consisting of a list of 12 nouns (targets) with four words drawn from each of three semantic categories. The semantic categories differ across the six forms, but the forms are very similar in their psychometric properties. The HVLT-R has high test-retest reliability, and its construct, concurrent, and discriminant validity have been well-established (Shapiro et al., 1999). Raw scores are derived for Total Recall, Delayed Recall, Retention (% retained), and a Recognition Discrimination Index. Verbal memory has been shown to be a cognitive domain negatively affected by HIV infection (Antinori et al., 2007; Robertson and Yosief, 2014; Woods et al., 2004). There are two primary outcomes: Total Recall and Delayed Recall. Task duration is 5-10 min with a 25-min delay.

Response Inhibition. The Stop Signal Task (SST) is a measure of response inhibition used in previous work with smokers and shown to be sensitive to abstinence ([name] and Hawk, 2012; Tsaur et al., 2015). In this task, participants are instructed to respond to left and right-facing arrows on the computer screen. Following practice trials, participants complete three 64-trial task blocks with stop signals (an 800-Hz, 100-ms, 70-dB tone) presented on 25% of trials. The initial stop delay in each block is 250ms and adjusts  $\pm 50$ ms depending on whether the participant successfully inhibits (Logan et al., 1997). Trials consist of a 500-ms warning stimulus, a 1,000-ms go signal (left- and right-facing arrows), and 1,000-ms blank screen inter-trial interval. The primary outcome is stop signal reaction time (SSRT), calculated as the mean RT on go-trials (MRT) minus mean stop delay (MSD). Task duration is 10 min.

**Delay Discounting Task.** In this paradigm, participants choose between a smaller reward available immediately (e.g., \$500 today) and a larger reward available after a longer delay (e.g., \$1000 in a month). In this task, people differ in their degree of *delay discounting*, the extent to which they forgo larger monetary magnitudes in the future in order to obtain immediate rewards. As in previous work, the delayed reward will be fixed (e.g., \$1000) and the magnitude of the immediate reward adjusts based on the subject's responses (Du et al., 2002). Subjects will make 42 choices (6 trials for each of 7 delays: 1 day, 1 week, 1 month, 3 months, 1 year, 5 years, and 25 years). The primary behavioral outcome will be the subject's *discount rate*. Discount rates will be estimated by fitting a logistic regression that assumes a person's decisions are a stochastic function of the difference in subjective value between the two options (Wileyto et al., 2004). Keeping with standard behavioral findings (Kable and Glimcher, 2007, 2010; Kirby and Santiesteban, 2003; Mazur, 1987), we will assume that subjective value (SV) is a hyperbolic function of the reward amount (A) and delay (D):  $SV = A/(1+kD)$ , where  $k$  is the participant's discount rate. Larger values of  $k$  indicate a greater degree of discounting future rewards. Participants will be told that the questions are hypothetical and that they should make their choices according to what they would choose if they were going to receive that amount. Task duration: approximately 5 minutes.

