**Aim 1.** We will analyze neurocognitive data with multiple linear regression using a GLM framework. The outcomes will be cognitive deficits measured as a change in response values (see **Section D.4.d.** for description) due to abstinence challenge (24-h abstinence vs. smoking-as-usual). The hypothesized interaction effect of HIV+ status by abstinence condition will be tested by including dichotomous predictors, and examining the corresponding *z*-score. Although the groups will be matched on key variables, we may also include a small number of covariates (e.g., nicotine dependence, Shipley IQ) that show potential to control for error, admitted to the model at  $p=0.1$ . In conjunction with Aim 1, we will be estimating cognitive measures for the HIV+ group, within-subject correlations, and deficits that arise from abstinence challenge. We will summarize point estimates and provide 95% confidence intervals.

**Aim 2.** We will analyze point-prevalence quit rates using logistic regression. The hypothesized effect of HIV status (HIV+ vs. HIV-) will be tested by including a dichotomous term using the *z*-score. A small number of other potential controlling variables will be tested for inclusion ( $p=0.1$ ). Outcomes of the logistic regression analyses will be characterized by odds ratios (e.g., odds of quitting smoking) and 95% confidence intervals. Point-prevalence quit rates at EOT are the primary outcome. Secondarily, we will conduct logistic regression analyses for other assessments of quit rates, including prolonged and continuous abstinence.

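### SSRT is scored as mean go RT minus mean stop delay while the delay restarts every 16 stop trials, so it rises with go-RT slowing and could mimic an HIV-by-abstinence effect if slowing differs by HIV status

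*Combined protocol and SAP*

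**What the plan says.** The combined protocol and SAP describes the stop-signal task under Neurocognitive Outcomes, Response Inhibition. After practice, "participants complete three 64-trial task blocks with stop signals" "presented on 25% of trials". On the staircase it says "The initial stop delay in each block is 250ms and adjusts" by 50 ms up or down, "depending on whether the participant successfully inhibits". Go trials use "a 1,000-ms go signal (left- and right-facing arrows". On scoring it says "The primary outcome is stop signal reaction time (SSRT", "calculated as the mean RT on go-trials (MRT) minus mean stop delay (MSD".

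The section gives no other scoring rule, no discarding of the first stop trials in a block, no check that the stop-failure rate is near 50%, and no handling of a change in go RT between sessions.

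Under Data Analysis, Aim 1: "The outcomes will be cognitive deficits measured as a change in response values" between the abstinent and smoking-as-usual sessions, with a test of whether that change differs by HIV status. Power Analysis and Sample Size gives five cognitive measures, each tested at alpha 0.01, with 150 per group and 80% power for d = 0.4. Aim 3 uses five task measures, as differences, as candidate mediators. Neither place names the five.

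**The concern.** Mean go RT minus mean stop delay estimates SSRT when the average delay sits where a participant fails to stop about half the time. Here the delay returns to 250 ms three times per session. When a participant's go RT is well above 250 ms plus SSRT, the trials after each restart use delays that are too short, so too little is subtracted. If go RT lengthens between sessions, the mean delay follows only part of the way and SSRT rises although inhibition has not changed.

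The Aim 1 outcome is a change between a smoking and an abstinent session, and abstinence may slow responding. If it slows HIV+ smokers more, general slowing would be scored as poorer response inhibition, in the direction of the study hypothesis, and could enter the Aim 3 path model as an inhibition pathway. The protocol's own Background makes differential slowing plausible without quantifying it: it cites processing-speed deficits in HIV and attention deficits in abstinence, and proposes that HIV-related and abstinence-related impairments may compound each other.

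**Working it through.** **Inputs from the plan.** Stop trials per block: 64 × 0.25 = 16, so 48 in all, with 192 − 48 = 144 go trials. Start 250 ms, step 50 ms, go window 1,000 ms. Aim 1: 150 per group, alpha 0.01 (two-sided assumed; the plan does not say), d = 0.4.

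**Assumed, because the plan gives no RT or SSRT values.**
- Set A: right-skewed (ex-Gaussian) go RTs, SD 110 ms with an exponential part of 80 ms; true SSRT mean 230 ms, SD 30 ms.
- Set B: normal go RTs, SD 100 ms; true SSRT 220 ms; between-subject go-RT SD 70 ms.
- SD of true SSRT change between sessions: 0 to 60 ms.

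**1. The plan's own figure.** Power for Aim 1 = Φ(d√(n/2) − 2.576) = Φ(0.4 × √75 − 2.576) = Φ(0.888) = 0.81. This agrees with the stated 80%. The plan states no SSRT figure to reproduce.

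**2. The run-in by hand (SSRT 220 ms).** The 50% point is roughly go RT minus SSRT. Take the fastest possible climb from 250 ms.
- Go RT 550: target 330; shortfalls 80 + 30 = 110 ms; 110/16 = 6.9 ms per stop trial.
- Go RT 650: target 430; shortfalls 180 + 130 + 80 + 30 = 420 ms; 420/16 = 26.3 ms.
- Slope: (26.3 − 6.9)/100 = 0.19 ms of SSRT per ms of go RT. Early stop failures lengthen the climb and add to the bias.

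**3. Simulated bias.** Set B, true SSRT 220: the written score averages 207, 217, 225, 235, 246, 258 and 272 ms at go RT 400, 450, 500, 550, 600, 650 and 700. From 450 to 650 the slope is (258 − 217)/200 ≈ 0.21; with right-skewed go RTs it is about 0.17. The score is unbiased near 250 + 220 = 470 ms and too low for faster responders.

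Set A:

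| Go RT (ms) | Mean-method bias (ms) | Integration bias (ms) |
|---|---|---|
| 450 | +1 | −4 |
| 550 | +18 | −1 |
| 650 | +37 | +4 |
| 750 | +62 | +19 |

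The staircase does converge inside each block. Under Set A the probability of responding on a stop trial is 0.38 (go RT 550) and 0.18 (650) in trials 1–4, but 0.47–0.50 in trials 9–16 at 550, 650 and 750. The bias comes from the repeated run-in.

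**4. False interaction, no true SSRT effect, 150 per group, alpha 0.01, 400 replicates.** Set B has both groups at 520 ms, with slowing of 10 ms in HIV− and 30, 40 or 60 ms in HIV+.

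| Extra HIV+ slowing | Set A, SD of true change 0 / 35 / 60 | Set B, SD 0 / 30 |
|---|---|---|
| 20 ms | 8% / 6% / 4% | 13% / 3% |
| 30 ms | 24% / 9% / 5% | 20% / 13% |
| 50 ms | 75% / 38% / 16% | 75% / 46% |

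Hand check (Set B, 50 ms, SD 30): false difference 10.13 ms, change-score SD 35.7 ms, SE = 35.7 × √(2/150) = 4.12, and Φ(10.13/4.12 − 2.576) = Φ(−0.12) = 0.45. At 50 ms the spurious d is 0.20 to 0.38, against the 0.4 the trial is powered for.

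Equal slowing of 20 ms in both groups gives 1.0–1.5%, and 1.2–1.8% when HIV+ also start 50 ms slower.

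**5. Integration scoring, same data.** The false-positive rate is 5% or less throughout Set A and 1.0–3.5% in the Set B cells above. It is not zero-bias: if HIV+ start 50 ms slower and also slow by 50 ms more, Set B gives 61–90% with the written score and 6–15% with integration.

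**The case against.** **The staircase works.** A reader might infer that the delay never catches up in slower responders. Step 3 shows that it does, by the second half of each block. This part of the objection stands, and it locates the cause in the restarts. Mean scoring with the delay carried across blocks gave a false-positive rate of only 1–6% for 50 ms of extra slowing from equal baselines.

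**Aim 1 tests an interaction.** A reader might infer that any abstinence slowing produces a false HIV effect. It does not: slowing common to both groups leaves the error near 1–2%, even with a slower HIV+ baseline. The problem needs slowing that differs by HIV status, and the documents report none.

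**SSRT may not be among the five.** The Aim 1 hypothesis names verbal and working memory, and Overall Objectives mentions response inhibition under the Exploratory Aim. The task descriptions list seven primary scores: two for N-back, one for Stroop, two for HVLT-R, SSRT and the discount rate. Against that, exactly five tasks are described, and SSRT is the only primary score of one of them. Inclusion is likely but not stated. Aim 3 is also conditional on a significant Aim 2 result.

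**Comparability.** The section says the task was used in earlier abstinence studies. That is a reason to keep reporting the mean-method score, not a reason to leave it as the only one.

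**Conclusion.** The scoring rule and the restart are as written, and together they make SSRT rise with go RT at roughly 0.17–0.21 ms per ms. The positive direction follows from the task rules; the slope depends on assumed RT distributions and is steeper at long go RTs. The consequence for Aim 1 is conditional. With extra HIV+ slowing of 20, 30 or 50 ms the false-positive rate is about 3–13%, 5–24% or 16–75% instead of 1%, the range reflecting an SD of true SSRT change of 0 to 60 ms; a larger SD dilutes it. The documents do not support saying that such slowing will occur, or that a positive SSRT finding would be false. They support saying that, as planned, slower responding and poorer inhibition could not be told apart on this measure. The change should be made before the data are analysed.

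**What to change.** - Make integration-method SSRT the main score: from each session's trial-level data, take the go RT at the percentile equal to the proportion of stop trials with a response, and subtract the mean stop delay. State in advance how go omissions are handled, for example counted at the 1,000-ms limit.
- Keep the mean-method SSRT as a sensitivity analysis for comparability with earlier work.
- Report mean go RT and the stop-failure rate by group and session, so that differential slowing is visible.
- Name the five Aim 1 measures and Aim 3 mediators.

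**Cost.** Existing files are re-scored, with no new testing. The single-score SD rises from about 19 to 22 ms. Part of that rise is signal. In Set B, adding a 30 ms SD of true change raises the change-score SD from 26.7 to 35.7 ms with the mean method, which implies √(35.7² − 26.7²)/30 = 0.79 ms per ms of true change. With integration it rises from 29.6 to 40.9 ms, which implies √(40.9² − 29.6²)/30 = 0.94. Signal per unit SD is 0.79/35.7 = 0.022 against 0.94/40.9 = 0.023, so under these assumptions power for a true effect is not lost. A residual false-positive rate of about 2–5% remains in most differential-slowing scenarios, and more in the extreme case of step 5, which is why go RT has to be reported alongside.

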### **Outcomes Variables.**

#### **Abstinence (primary).**

Smoking status will be assessed using the reliable and valid timeline follow-back method (Brown et al., 1998) and by using CO breath samples to biochemically verify the self-report as in prior work (Lerman et al., 2004; Lerman et al., 2015; Schnoll et al., 2015; Schnoll et al., 2010). Participants will be considered to be abstinent if they self-report abstinence (not even a puff of a cigarette) for  $\geq 7$  days prior to each assessment beginning 1-week post-TQD (week 4) and provide or report a CO measurement of less than 5 ppm (Cropsey et al., 2014; Perkins et al., 2013). As per convention, participants are assumed to be smoking if they self-report smoking, cannot be reached to provide data at the time-point, fail to provide a breath sample at the time-point, or provide a breath sample at the time-point  $\geq 5$  ppm (Cropsey et al., 2014; Perkins et al., 2013). The primary outcome will be 7-day point-prevalence abstinence at EOT.

#### **Other Smoking Measures (secondary).**

The total number of days abstinent during the first 7 days following the TQD, confirmed with CO, will be a secondary outcome measure. We have shown that this measure is highly predictive of long-term abstinence ([name] et al., 2013b). Other secondary smoking outcomes include: prolonged abstinence to EOT (week 12) where relapse is 7 consecutive days of self-reported smoking, after a 2-week grace period; continuous abstinence at EOT (no smoking between the TQD and the follow-up; time to 7-day relapse (no grace period); and lapse (smoking episodes not lasting 7 days) and recovery (return to 24-hour abstinence) events (see (Schnoll et al., 2010)).

**Cessation/Smoking Rate:** Daily smoking (presence and rate) will be assessed at each visit after the Intake Session with the well validated timeline follow-back method (TLFB). These data can be used to assess the timing and rates of lapses (smoking episodes not lasting 7 days), recovery events (return to abstinence), and relapse events, as well as to monitor changes in smoking rates (i.e., # cigarettes/day). These data will also be used to compute and assess secondary measures of smoking cessation (e.g., continuous and prolonged abstinence).

**Carbon Monoxide (CO) Test:** Carbon monoxide will be measured by staff at Intake and the Lab sessions. Following Lab session 2, subjects will be asked to self-report their CO levels using an iCO device (carbon monoxide reader) that will be provided to them at Lab session 2. The iCO smokerlyzer (CoVita, Santa Barbara, CA) is a personal breath smokerlyzer monitor for use with a smartphone or tablet. It works in conjunction with the Smokerlyzer app on iOS and android phones or tablets. The iCO device provides biofeedback from a simple breath test, and it also allows users to track their progress. The app also provides an exhalation guide to coach users on the proper technique to ensure accurate results. The device can be connected to the users' phone through the headphone jack or via Bluetooth. Participants with iOS devices who require adapters will be provided with them by staff. Participants who do not have a smartphone or tablet, or are unable to use the device, will be asked to report to our center for a carbon monoxide assessment if they report abstinence. Since the iCO device cannot be sanitized and does not come with changeable mouthpieces, participants will be advised to limit use of the device to only themselves.

